10.6.4 Columbia-Suicide Severity Rating Scale (C-SSRS)

No statistical testing will be performed on C-SSRS. The number and percentage of subjects reporting any suicidal ideation and any suicidal behavior will be summarized descriptively by treatment group separately for the DBTP and OLTP. Shift table of C-SSRS maximum severity of suicidal ideation/behavior compared to baseline will be provided by treatment group separately for the DBTP and OLTP.

10.6.5 Electrocardiogram (ECG)

The ECG measurements from this clinical study were performed as per standard of care for routine safety monitoring, rather than for purposes of assessment of potential QTc effect. Since these evaluations may not necessarily be performed under the rigorous conditions expected in a thorough QT study, neither summaries nor statistical analyses for QTc will be provided, and these data are not expected to be useful for meta-analysis with data from other trials.

Subject incidence of ECG diagnosis will be summarized by treatment group separately for the DBTP and OLTP.

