6.3 Study Points of Reference

Baseline Assessment

Baseline assessment is defined as the last non-missing measurement for the endpoint of interest taken before the first dose of investigational product. In cases where baseline measurements are taken on the same day as IP, it will be assumed that these measurements are taken prior to IP being administered. For subjects who are randomized but not dosed after the randomization, the baseline of the study is defined as the last non-missing measurement prior to or on the date of randomization.

For C-SSRS, if subject completes C-SSRS form on Day 1 then all individual items from Day 1 visit will be used as baseline. If subject does not complete C-SSRS form on Day 1 then all individual items from Week -4 visit will be used as baseline.

Baseline assessment of data collected from eDiary will be summarized as monthly measurements using data collected during baseline period. See [Section 6.1.1](#) for detail.

Study Day 1

Study Day 1 is defined as the first IP dose date. For subjects who are randomized but not dosed after randomization, the Study Day 1 is defined as the date of randomization.

Study Day

Study Day is defined as the number of days from Study Day 1.

Before Study Day 1:

Study Day = (Date of Interest – Date of Study Day 1)

On or after Study Day 1:

Study Day = (Date of Interest – Date of Study Day 1) + 1

Therefore the day prior to Study Day 1 is -1.

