Open-label Treatment Phase	Week 28	
• The 1st OL dose day	
• Week 28 dose date-1• OLTP day 28 if Week 28 dose is not received (either missed or IP discontinued prior to Week 28)

	Week 32 or later when eDiary is used	
• Same rule as above	
--	--------------------------------------	--	--

Study Visit

Since the actual visit for a subject may not exactly coincide with their targeted visit date, the actual visit date is mapped to the study visit as follows.

Study Visit	Target Day	Study Day
Baseline		Please refer to Section 6.3 Baseline Assessment of the Study
Day 1	1	1
Week 4	29	16-43
Week 8	57	44-71
Week 12	85	72-99
Week 16	113	100-127
Week 20	141	128-155
Week 24	169	
• 156 to (week 24 OLTP dose date – 1) for subjects who receive OLTP dose at week 24• 156-183 for subjects who did not receive OLTP dose at week 24
Week 28	197	
• Week 24 OLTP dose date to 211 for subjects who receive OLTP dose at week 24• 184-211 for subjects who received at least one OLTP dose and did not

		receive OLTP dose at week 24 (e.g., first OLTP dose was postponed)
Week 32	225	212-239
Week 36 to Week 72	Following same monthly windowing as Week 32	
Safety follow-up	Based on visit name from RAVE or other source data	

Note:

If more than one visit (including the unscheduled visits, ie, CPEVENT = 'UNSCHED') fall within the same defined window, scheduled visit will be used regardless of the distance from the target day. Unscheduled visit will only be used when there is no scheduled visit in the defined window. The closest visit to the target day among the same type of visit (scheduled vs. unscheduled) will be considered for analysis. If two assessment dates are equidistant from the target date, the latter visit will be considered for analysis.

For safety analyses which are summarized by study phase, analysis windows will be set up based on study phase:

Study Phase	Start Time Point	End Time Point
Double-Blind Treatment Phase	Study Day 1 after the 1 st DB IP Dose	
First OL Dose Date for subjects who receive OL IP dose;Min(EOS Date, last IP dose date + 112 days) for subjects who do not receive any OL IP dose
Open-Label Treatment Phase	1 st OL IP Dose Date	Min(EOS Date, last OL IP dose date + 112 days)

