- Change from baseline in monthly bed days due to migraine related symptoms
- Change from baseline in monthly missed work/school days due to migraine related symptoms
- Change from baseline in monthly headache impact scores as measured by HIT-6

Mean Change from Baseline in Monthly Efficacy Measurement over multiple months

The Mean Change from Baseline in Monthly Efficacy Measurement is the Arithmetic mean of each change from baseline value for the months considered

Percent Change from Baseline

The change from baseline divided by baseline and multiplied by 100:

$$(\text{Post-baseline} - \text{Baseline}) * 100 / \text{Baseline}$$

If the baseline value is 0 and the post-baseline value is also 0, then the percent change from baseline is set to 0. If the baseline value is 0 and the post-baseline value is non-zero, then the percent change from baseline is set to missing.

Percent change from baseline in (mean) monthly migraine days which is used to determine 50%, 75%, and 100% responder will be calculated as above.

Subject Incidence

The subject incidence for a given event in a given period is defined as the number of subjects with at least one reported occurrence of the event divided by the number of subjects who entered that period. For subjects with multiple occurrences of the same event, the event will only be counted once per subject.

Exposure-Adjusted Incidence Rate

The exposure-adjusted incidence rate for a given event in a given period is defined as the number of subjects with at least one reported occurrence of the event in a given time period at risk divided by total exposure time of all subjects who are at risk for the event.

For subjects with events, only the time until the first event contributes to the total exposure time. For subjects with no event, the exposure time is the time from the first IP dose to the last follow-up assessment. This rate will be presented per 100 subject years. For subjects with multiple occurrences of the same event, the first occurrence of an event will be counted for each subject.

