10.6.3 Vital Signs

The analyses of vital signs (systolic/diastolic blood pressure and weight) will include summary statistics of change from baseline over time by treatment group.

Systolic blood pressure and diastolic blood pressure may be analyzed by change from baseline in categories: 10-20 mmHg and \geq 20 mmHg and analyzed for SBP >140 mmHg (Yes vs. No) and DBP > 90 mmHg (Yes vs. No) at each time point.

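### SAP 10.6.5 counts ECG diagnoses as incidence in each phase without reference to the pre-dose ECG, so long-standing diagnoses appear as on-treatment events

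*SAP*

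**What the plan says.** SAP 10.6.5 rules out QTc summaries and plans one ECG output: "Subject incidence of ECG diagnosis will be summarized by treatment group separately for the DBTP and OLTP". SAP section 14 confirms that ECG interval data are not analysed.

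SAP 6.6 defines subject incidence, for a given event and period, as "the number of subjects with at least one reported occurrence of the event divided by the number of subjects who entered that period". The double-blind safety window in SAP 6.4 opens at "Study Day 1 after the 1 st DB IP Dose", and the open-label window opens at the first open-label dose.

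SAP 6.3 supplies a baseline: "Baseline assessment is defined as the last non-missing measurement for the endpoint of interest taken before the first dose of investigational product". Section 10.6.5 does not use it. Protocol 10.5.5 contains no rule for ECG analysis.

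For blood pressure, SAP 10.6.3 commits to analyses that "will include summary statistics of change from baseline over time by treatment group". It then adds an option: "Systolic blood pressure and diastolic blood pressure may be analyzed by change from baseline in categories: 10-20 mmHg and" a second class of 20 mmHg or more. The option also includes a Yes/No split at 140 mmHg systolic and 90 mmHg diastolic at each time point.

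**The concern.** Incidence in a safety table is normally read as something that arose on treatment. The safety window restricts when a tracing was taken, not whether the diagnosis on it is new. A subject who enters with a stable, minor ECG diagnosis will usually have it read again after dosing, and the rules then count that subject.

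The result is a mixture of prevalence and new onset under the label of incidence. In the double-blind phase, new diagnoses of a given type are set against a background of old ones. In the open-label phase every subject receives AMG 334, so pre-existing diagnoses can be mistaken for events on the drug. Because intervals are not analysed, no other ECG table would put this right.

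**Working it through.** **Can a pre-existing diagnosis enter the count?**

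1. Entry. Exclusion 217 removes only abnormalities that the investigator considers clinically significant and a possible risk or interference. Other ECG diagnoses can enter.
2. Pre-dose tracings. Protocol Table 2 schedules ECGs at initial screening and on Day 1. Protocol 7.2.23 places the first dose after all Day 1 procedures, and SAP 6.3 treats same-day measurements as pre-dose. A baseline ECG is therefore available.
3. Post-dose tracings. Table 2 has ECGs at weeks 4, 8, 12 and 24, and Table 3 repeats them through the open-label phase. Protocol 7.2.10 has a central reader review all of them.
4. Counting. Under SAP 6.6 one post-dose reading in a phase is enough. A stable diagnosis scores once in the double-blind phase and once in the open-label phase.

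**How does the SAP treat comparable data?** Treatment-emergent adverse events must start on or after first dose (SAP 6.1.2). Neutrophil counts have a shift table relative to baseline (SAP 10.6.2). The C-SSRS has one too (SAP 10.6.4). ECG diagnosis has neither a baseline condition nor a shift table.

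**Illustration of size.** The documents state no ECG figure to reproduce, so all rates here are assumptions. For one specific diagnosis, let b be the share of subjects who have it before dosing and in whom it is read again afterwards, and p the new-onset risk among the rest. The planned table shows b + (1 − b) × p. Take p = 2% on placebo and 4% on active, a true ratio of 2.00.

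| b | Placebo: b + (1 − b) × 0.02 | Active: b + (1 − b) × 0.04 | Ratio | Difference (points) | Placebo count already present (b ÷ placebo) |
|---|---|---|---|---|---|
| 0% | 2.00% | 4.00% | 2.00 | 2.00 | 0% |
| 1% | 2.98% | 4.96% | 1.66 | 1.98 | 34% |
| 2% | 3.96% | 5.92% | 1.49 | 1.96 | 51% |
| 5% | 6.90% | 8.80% | 1.28 | 1.90 | 72% |
| 10% | 11.80% | 13.60% | 1.15 | 1.80 | 85% |
| 20% | 21.60% | 23.20% | 1.07 | 1.60 | 93% |

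With the planned 131 per arm and b = 5%, the table would show about 131 × 0.069 = 9.0 placebo and 131 × 0.088 = 11.5 active subjects. Of these, 131 × 0.95 × 0.02 = 2.5 and 131 × 0.95 × 0.04 = 5.0 are new. The rates and the ratio change substantially, while the absolute difference shrinks only by the factor 1 − b.

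With lower onset, 1% against 2%, the ratios at b = 1%, 2%, 5%, 10% and 20% are 1.50, 1.33, 1.16, 1.08 and 1.04.

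In the open-label phase the same formula applies with no comparator. With b = 5% and 2% new onset, the table shows 0.05 + 0.95 × 0.02 = 6.9%, and nothing in it separates the two parts.

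**Blood pressure classes.** A change of exactly 20 mmHg satisfies both optional classes. If changes are normal with mean 0 and SD 10 to 12 mmHg (assumed) and recorded as whole numbers, about 0.5% to 0.8% of readings are exactly +20. Protocol 7.2.6 records the average of at least two readings. If averages of two are kept to 0.5 mmHg, the share is about 0.27% to 0.41%. The documents do not say whether averages are rounded.

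**The case against.** The strongest reply is that clinically relevant new findings do not depend on this table. The investigator must evaluate abnormalities noted by the central reader (Protocol 7.2.10) and judge ECG findings against the subject's own baseline (Protocol 9.2.1). Those needing treatment or a change in therapy become adverse events. Treatment-emergent events are tabulated by group and phase, and potential cardiovascular events go to blinded adjudication (Protocol 9.3). This stands. It limits the harm, but it does not make the ECG table show what its label says.

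Second, randomisation balances pre-existing diagnoses on average. This also stands: a reader might infer a bias for or against AMG 334 in the double-blind comparison, and none is expected. The effect there is inflated rates and a diluted ratio.

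Third, SAP 6.6 speaks of a given event, so an old diagnosis dilutes only its own row, and a new diagnosis of a different kind appears separately. This is right. It is why the illustration is per diagnosis and includes prevalences as low as 1%. It does not support an inference that new findings generally would be hidden.

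A reader might also infer that the blood pressure thresholds suffer the same fault. The documents do not support that. The split, "analyzed for SBP >140 mmHg (Yes vs. No) and DBP > 90 mmHg (Yes vs. No) at each time point", is optional, is not called incidence, and is a valid point prevalence at each visit. It sits beside firmly planned change-from-baseline summaries. Whether to show it next to baseline status is a presentation choice. Nor is it certain that anyone with a +20 mmHg change will be counted twice, since the classes belong to an analysis that may not be run.

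**Conclusion.** The point holds for ECG diagnoses. Followed as written, SAP 10.6.5 with SAP 6.6 reports pre-existing diagnoses as on-treatment incidence in each phase, and no other section corrects this. Rates are inflated and ratios for the affected diagnosis are diluted in the double-blind phase. In the open-label phase old and new cannot be separated.

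The importance is minor. This is a descriptive safety table, SAP 10.6 excludes statistical testing of safety, and the primary analysis is untouched. The size is illustrative only: it rests on assumed prevalence and onset, and on the diagnosis being read again after dosing. The direction, inflation and dilution, holds for any prevalence above zero when the true ratio differs from 1.

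For blood pressure, the only defect is the overlapping boundary at 20 mmHg, which is editorial.

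**What to change.** In SAP 10.6.5, tabulate each ECG diagnosis as new relative to the SAP 6.3 baseline, with subjects free of that diagnosis at baseline as the denominator. For the open-label phase, also flag diagnoses that were absent before the first open-label dose. The week 24 ECG can serve, since Protocol 7.2.24 places that dose after all week 24 procedures. Alternatively, add a baseline by worst post-baseline shift table for each phase.

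In SAP 10.6.3, write the optional change classes as at least 10 to under 20 mmHg, and at least 20 mmHg.

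The cost is a few lines of SAP text and a programming filter. The baseline ECGs and blood pressures are already collected, and sample size, power and alpha do not change.

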10.6.6 Antibody Formation

The number and percentage of subjects who develop anti-AMG 334 antibodies (binding and, if positive, neutralizing) will be tabulated by treatment group for the entire study.

The list of subjects with positive antibodies at any time will be provided.

In addition, a listing of treatment-emergent AEs will be provided for subjects with positive binding or neutralizing antibodies.

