10.5.5 Safety Endpoints

For safety endpoints, all randomized subjects who received at least one dose of investigational product (ie, safety analysis set) will be analyzed **according to the randomized treatment unless a subject has received the incorrect dose during the entire double-blind treatment phase.**

The Medical Dictionary for Regulatory Activities will be used to code all adverse events.

Subject incidence rates (double-blind treatment phase) and **exposure-adjusted** subject incidence rates (**OLTP**) of all treatment-emergent adverse events will be tabulated by treatment groups and by system organ class and preferred term. Tables of fatal adverse events, serious adverse events, adverse events leading to withdrawal from investigational product, treatment-related adverse events, serious treatment-related adverse events, and adverse events of special interest also will be provided.

In addition, summaries of treatment-emergent adverse events and summaries of serious treatment emergent adverse events will be provided by preferred term in descending order of frequency. The analyses of safety laboratory endpoints will include summary statistics over time by treatment group **for selected analytes**. Shift tables of the worst on-study safety laboratory toxicity based on grade relative to baseline will be tabulated by treatment group.

The analyses of vital signs will include summary statistics over time by treatment group.

The incidence and percentage of subjects who develop anti-AMG 334 antibodies (binding and if positive, neutralizing) at any time will be tabulated by treatment group.

All safety analyses will be performed for the double-blind treatment phase and **OLTP** separately.

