3.1.2 Open-Label Treatment Phase

At the week 24 visit, subjects will be entered into the 52-week OLTP and will begin to receive open-label AMG 334 70 mg QM SC.

A subject who discontinues open-label investigational product or the study during OLTP will complete the week 76/early termination (ET) visit and the safety follow-up visit 16 weeks after the last dose of investigational product.

Subjects will use eDiary every day for the first 6 months and last month of the OLTP to report information about their migraine and non-migraine headaches and acute headache medication use. Subjects will participate in monthly in-clinic study visits.

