Entire Study	Study Day 1 after the 1 st DB IP Dose	Min(EOS Date, last IP dose date + 112 days)

Note: all antibody data will be included in antibody analysis.

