10.7.1 Exposure-Response Analysis

Exposure-Response (E-R) analysis will be performed. Please refer to the E-R SSAP for additional details.

11. Changes from Protocol-specified Analyses

N/A

12. Literature Citations / References

- Fitzmaurice GM, Laird NM and Ware JH. (2004). Applied Longitudinal Analysis. New York: John Wiley and Sons.
- Breslow, N. E. and Clayton, D. G. (1993), Approximate Inference in Generalized Linear Mixed Models, *Journal of the American Statistical Association*, 88, 9–25.
- Wolfinger, R. and O'Connell, M. (1993), Generalized Linear Mixed Models: A Pseudo Likelihood Approach, *Journal of Statistical Computation and Simulation*, 4, 233–243.
- Rubin, D. B. (1987), Multiple Imputation for Nonresponse in Surveys, New York: John Wiley & Sons, Inc.
- Heinze, G. and Schemper, M. (2002), A Solution to the Problem of Separation in Logistic Regression, *Statistics in Medicine*, 2002; 21:2409–2419.
- Quade, D. (1966), Rank analysis of covariance, University of North Carolina, Institute of Statistics Mimeo Series. No. 483
- Fairclough DL1, Cella DF. Functional Assessment of Cancer Therapy (FACT-G): non-response to individual questions. *Qual Life Res*. 1996 Jun;5(3):321-9.

13. Prioritization of Analyses

The tables, listings and figures for Flash Memo of primary analysis at week 24 will be prioritized.

14. Data not Covered by This Plan

There are no plans to specifically analyze or summarize the following data points.

- ECG interval data
- PK
- CCI [REDACTED]
- CCI [REDACTED]

15. Appendices

Appendix A. Technical Detail and Supplemental Information Regarding Statistical Procedures and Programs

A1 Generalized Linear Mixed Model

Generalized mixed effects repeated measure model fits data with correlations or nonconstant variability and where the response is not necessarily normally distributed, which is also known as generalized linear mixed models (GLMM). The correlations can arise from repeated observation of the same sampling units, shared random effects in an experimental design, spatial (temporal) proximity, multivariate observations, and so on.

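### SAP 10.6.6 tabulates antibodies only over the whole study, so positives arising on open-label AMG 334 are counted under placebo and no table covers the placebo-controlled period

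*SAP*

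**What the plan says.** Protocol 10.1.1.2 and SAP 4.1.2 both list anti-AMG 334 antibodies among the secondary safety endpoints.

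SAP 10.6.6 plans one incidence table for binding and, where positive, neutralising antibodies; the counts "will be tabulated by treatment group for the entire study". It adds a listing of positive subjects and a listing of their treatment-emergent adverse events. The note under the safety windows in SAP 6.4 rules out any cut by phase: "all antibody data will be included in antibody analysis".

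Protocol 10.5.5 has two relevant sentences. One concerns antibodies: subjects who develop them "at any time will be tabulated by treatment group". The other closes the section and covers everything in it: "All safety analyses will be performed for the double-blind treatment phase and" the open-label treatment phase (OLTP) separately. It makes no exception for antibodies.

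SAP section 11, headed "Changes from Protocol-specified Analyses", has the entry N/A.

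**The concern.** SAP 10.1 and 10.6 count subjects in their randomised group. The only exception is a subject given the incorrect dose for the whole period of interest, which planned open-label dosing is not. At Week 24, subjects "will begin to receive open-label AMG 334 70 mg QM SC" (SAP 3.1.2). Under Amendment 2 the open-label dose is 70 mg or 140 mg, depending on the subject's visit status. Either way, a placebo subject who continues is exposed to AMG 334, and a positive that first appears after that exposure falls in the placebo column.

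The active columns are affected too, wherever the open-label dose differs from the randomised dose. Under the SAP's design these are the 28 mg and 140 mg columns; the 70 mg column is not mixed. Under Amendment 2 the 28 mg column is always mixed, and the 70 mg and 140 mg columns depend on the open-label sequence.

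What is at stake is the drug-free background rate. The double-blind placebo arm is the only group that can supply it, and the planned table merges it with on-drug results.

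**Working it through.** The plan states no antibody rate, so there is no figure to reproduce. The check compares the texts, then counts doses and samples.

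**Is the whole-study table an isolated choice?** The SAP splits adverse events (10.6.1), laboratory results (10.6.2), C-SSRS (10.6.4) and exposure (10.6.7) by phase. For ECG it says: "Subject incidence of ECG diagnosis will be summarized by treatment group separately for the DBTP and OLTP" (10.6.5). Antibodies are pooled.

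**Can the two Protocol sentences be reconciled?** Yes. The antibody sentence can mean at any time within each phase, or it can describe an overall table added to the by-phase ones. Neither reading supports a whole-study table alone.

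**Does the protocol version explain the gap?** The SAP cites Protocol 1.0, while the supplied Protocol is Amendment 2. The Amendment 2 change log for 10.5.5 shows no substantive change to either sentence, so it does not.

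**AMG 334 doses to a placebo-arm subject**
- Double-blind phase: 0.
- SAP design, Weeks 24 to 72 every 4 weeks: (72 − 24)/4 + 1 = 13.
- Amendment 2, Weeks 24 to 96 every 4 weeks: (96 − 24)/4 + 1 = 19.

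**Scheduled post-baseline antibody samples, placebo completer**
- Before the first open-label dose (Protocol Table 2): Weeks 4, 12 and 24 = 3. Week 24 counts here because open-label dosing starts only after all Week 24 procedures (Protocol 7.2.24).
- After it, 52-week schedule (the superseded table shown in the Amendment 2 change log): Weeks 28, 36, 52, 76 and safety follow-up = 5. Share: 5/(3 + 5) = 63%.
- After it, Amendment 2 (Protocol Table 3): Weeks 28, 36, one at Week 48 or 52 (the column position is unclear in the extracted table), 76, 100 and safety follow-up = 6. Share: 6/(3 + 6) = 67%. The two visits that apply only to subjects raised from 70 mg to 140 mg are left out.

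**Illustrative effect on the placebo column**

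The planned arm size is 131. Assume 90% enter the open-label phase, and let r be the assumed proportion who first become positive there. Added positives = 131 × 0.90 × r = 117.9 × r.

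| Assumed r | Added positives | Share of 131 |
|---|---|---|
| 2% | 2.4 | 1.8% |
| 5% | 5.9 | 4.5% |
| 10% | 11.8 | 9.0% |

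With entry between 80% and 95%, the limits are 0.80 × 2% = 1.6% and 0.95 × 10% = 9.5%.

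**The case against.** The best defence is that SAP 10.6.6 implements the one Protocol sentence written for antibodies, and that a specific sentence outranks a general closing rule. On that reading the N/A in section 11 is correct. Pooling also has a purpose: Protocol 7.3 has subjects with neutralising antibodies retested about every 3 months, for up to a year or more after the last dose, and the 112-day phase windows would miss those samples. Placebo is only a background check for an antibody endpoint, no safety testing between arms is planned, and every positive subject is listed.

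Part of this stands. The Protocol wording is loose, and the whole-study table is worth keeping. The rest does not answer the point. The two Protocol sentences are compatible, and honouring both requires by-phase tables. A listing is not an incidence by arm and phase. A background check is of little use once most of its samples are taken on drug.

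Two further objections:

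- **Timing.** The primary analysis runs when the last subject reaches Week 24, so its antibody table might in practice be close to double-blind. The SAP states no such cut, and subjects randomised early may already have open-label samples. It is fair, though, that the 63% and 67% apply to a placebo completer at the final analysis; contamination at the primary analysis would be smaller.
- **Vital signs.** SAP 10.6.3 does not mention phase either. But summaries over time already separate the periods, whereas one count of subjects ever positive cannot.

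**Conclusion.** The concern holds. Followed as written, the SAP gives a placebo column that includes antibodies arising on AMG 334 and no table for the controlled period. It also departs from the Protocol's by-phase rule without declaring it. The sample shares (63% and 67%) come from the visit schedules and assume a completer. The 1.6 to 9.5 percentage points rest entirely on assumed positivity and open-label entry rates and show scale only. The endpoint is descriptive, efficacy is untouched, and the split could be rebuilt by hand from the listing. This should be corrected, but it does not threaten the trial's main conclusion.

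**What to change.** Amend SAP 10.6.6 to tabulate binding and neutralising antibody incidence by phase, using the safety windows already in SAP 6.4:

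1. **Double-blind phase, by randomised group.** Include samples up to and including the pre-dose sample on the first open-label dose date. For subjects without open-label dosing, use the existing limit: "Min(EOS Date, last IP dose date + 112 days) for subjects who do not receive any OL IP dose".
2. **Open-label phase.** Include samples after the first open-label dose, by double-blind group and overall as in Protocol 10.4.4, and optionally by open-label dose.
3. **Whole study.** Keep the present table and listings as supplementary, including late follow-up samples.

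Three details need to be written down:

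- The first open-label dose date lies in both phase windows, so the text must assign that day's pre-dose sample to the double-blind phase.
- The study-visit table in SAP 6.4 ends Week 24 on the day before that dose and maps the dose date to Week 28. It needs the same exception if antibody results are shown by visit.
- Samples taken more than 112 days after the last dose can arise from the ±3-day visit window or from Protocol 7.3 follow-up. They will appear only in the whole-study table unless assigned by visit name.

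The cost is a few sentences and two descriptive tables, with no new sampling. If the sponsor prefers the whole-study table alone, section 11 should declare and justify the departure, but that would leave the placebo column contaminated.
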